### 1.3 Study Design and Dose Rationale

This is an open-label, single-arm, multi-center, phase II study of imlifidase added to standard care IVIg in subjects within 10 days of onset of GBS.

Approximately 30 subjects will be included in this study.

In addition to safety and tolerability, another objective of the proposed study is efficacy. Other objectives include pharmacokinetics (PK) and pharmacodynamics (PD).

Eligible subjects must have been diagnosed with GBS and be unable to walk unaided for >10 meters (grade  $\geq 3$  on Guillain-Barré Syndrome disability score (GBS DS)). Onset of weakness should be within 10 days before inclusion.

Healthy subjects have been dosed with 0.01-0.24 mg/kg, and patients up to 2 x 0.25 and 1 x 0.5 mg/kg of imlifidase. Rapid and complete cleavage of IgG to F(ab')2 and Fc fragments was demonstrated at a dose of 0.25 mg/kg. In this study, each patient will receive one dose of 0.25 mg/kg imlifidase administered as an intravenous infusion over 30 minutes on Day 1.

A standard 5-day IVIg regimen (0.4 g/kg/day for 5 consecutive days) will be initiated at least 48 hours after imlifidase dosing. As subjects will be included and dosed with imlifidase within 12 days of onset of weakness, IVIg treatment will be initiated in all subjects within 14 days from onset of weakness which is within the time frame for which standard treatment has been shown to have a beneficial effect on the outcome (Hughes et al. 2014).

[figure not shown]
Based on the current knowledge, including experience from completed and ongoing clinical studies, it is expected that imlifidase will degrade IgG into F(ab')2 and Fc fragments across all compartments allowing a rapid and potent inactivation of any pathological GBS auto-antibodies. This may in turn prevent irreversible nerve damage.

The hypothesis is that the reduction in pathological IgG antibodies may translate into aborted progression, quicker recovery and less severe disease as compared to standard treatment.

## 1.4 Benefit/Risk Aspects

The possible benefit for the subject is that the rapid depletion of the IgG pool will interrupt the progressive phase of the disease process and possibly lead to a more rapid and qualitatively better recovery than the standard of care treatment.

An imlifidase dose of 0.25 mg/kg has been selected for this study. The phase I study did not identify any dose limiting factors at the highest tested dose (0.24 mg/kg), and CKD patients in two completed phase II studies were exposed to up to 0.5 mg/kg with acceptable safety profiles.

In order to avoid pregnancies, a pregnancy test will be performed in women of child-bearing potential prior to dosing, and the requirement for highly effective contraception for all subjects is part of the inclusion criteria for this study.

One serious and four non-serious (one of which was in a subject treated with placebo) infusion related reactions regarded as related to treatment have occurred. Signs and symptoms associated with infusion related reactions included, but were not limited to dyspnoea, pharyngeal oedema, sinus tachycardia, chest discomfort and flushing.

To mitigate the risk of infusion related reactions, all subjects will receive methylprednisolone and antihistamine treatment prior to dosing and will be closely monitored during the infusion.

Since imlifidase effectively removes the IgG pool, there may be an increased risk of infection. To minimise the risk for bacterial infections all subjects treated with imlifidase will receive prophylactic antibiotics prior to imlifidase dosing. Subjects will be screened for Hepatitis B,

C, and HIV, and subjects having clinical signs of ongoing infection will be excluded from the study. Subjects will also be screened for SARS-CoV-2, and subjects with a positive test will not be included in the study. As SARS-CoV-2-naïve subjects do not have any IgG antibodies towards the virus, and since imlifidase does not prevent IgG synthesis, administration of imlifidase is not considered to have any impact on patient safety should the subject subsequently become infected with SARS-CoV-2. As IVIg treatment will be started at least 48 hours post dosing of imlifidase, normal IgG levels are expected to be restored shortly after and minimize the risk of infection.

In a previous study with imlifidase in patients with TTP, 2 patients developed rash and arthralgia, with one of the subjects experiencing fever as well. The sponsor cannot exclude that the underlying disease of TTP was a factor in the development of serum sickness in these patients since none of 27 other subjects treated with imlifidase without concomitant immunosuppression showed signs of serum sickness. Of note is that at the time of these events only very low levels of imlifidase were left in circulation, not sufficient to form immune complexes with Anti-Drug Antibody (ADA). Serum sickness has not been observed in toxicology studies.

The rationale for at least 48 hours between imlifidase and IVIg dosing is based on the pharmacokinetic and pharmacodynamic profiles of imlifidase. In addition, in one clinical study (14-HmedIdeS-04) alemtuzumab was given four days post dosing of imlifidase, and in another clinical study (15-HmedIdeS-06) IVIg was given seven days post dosing of imlifidase. As there is no data supporting initiation of IVIg treatment earlier than 48 hours post imlifidase dosing, a subject who deteriorates very quickly during the first 24 hours after imlifidase administration may be treated with PE to remove any remaining imlifidase before initiating IVIg treatment according to standard of care. This decision is made at the discretion of the investigator.

The subjects will be closely monitored for all adverse events. The principal investigators will make sure that sufficient facilities and procedures are available to handle emergency situations including unexpected adverse reactions during the study. Furthermore, all subjects will be included in a long-term safety follow-up approximately 12 months after dosing.

Adverse events after administration of IVIg do occur but are seldom serious. There is a very small risk of anaphylaxis, often in subjects with severe IgA deficiency. Other reported side effects include headache, myalgia, nausea, transient hypotension and flushing (all of which can be corrected by slowing the infusion rate), meningism, aseptic meningitis, skin reactions (especially eczema), neutropenia, worsening of renal failure, and thromboembolic events (Deep vein thrombosis (DVT), Myocardial Infarction (MI) and stroke) attributable to hyperviscosity (Hughes et al. 2014). To reduce the risk of thromboembolic events patients will be managed according to standard of care for GBS, i.e. patients who are unable to walk independently will receive subcutaneous low-molecular-weight heparin.

A guidance for the investigator and Reference Safety Information regarding imlifidase can be found in the Investigator's Brochure.

## 2. STUDY OBJECTIVES AND ENDPOINTS

### 2.1 Objectives

The objectives of this study are to:

- Assess safety and tolerability of imlifidase in combination with standard IVIg treatment in GBS subjects
- Evaluate pharmacokinetics of imlifidase
- Evaluate pharmacodynamics profile of imlifidase
- Evaluate immunogenicity of imlifidase
- Evaluate efficacy of imlifidase in subjects with GBS
- Evaluate quality of life after imlifidase treatment in subjects with GBS
- Evaluate healthcare resource utilization after imlifidase treatment in subjects with GBS
- Evaluate the contribution of a dose of imlifidase on outcomes with respect to severity of symptoms and recovery time through a comparison with an externally matched cohort of GBS subjects
- Evaluate the effect of imlifidase on exploratory biomarkers

### 2.2 Endpoints

The following endpoints will be evaluated:

- Type, frequency and intensity of AE / Serious Adverse Event (SAE) and change from baseline in parameters of clinical laboratory tests, vital signs and Electrocardiograms (ECG)
- Efficacy as assessed by:
  - Proportion of subjects with improvement of one or more grades in disability outcome (on the 6-point GBS DS) over time
  - Proportion of subjects with improvement of two or more grades in disability outcome (on the 6-point GBS DS) over time
  - Proportion of subjects with improvement of three or more grades in disability outcome (on the 6-point GBS DS) over time
  - Change in GBS DS over time
  - Proportion of subjects able to walk unaided (GBS DS  $\leq 2$ ) over time
  - Time to improvement by at least one, two and three grade(s) on the GBS DS
  - Time to walk independently (GBS DS  $\leq 2$ )

[figure not shown]
- Time to run (GBS DS  $\leq$  1)
- Proportion of subjects that reach GBS DS  $\leq$  1 by week 26
- Proportion of subjects with an increase from baseline in R-ODS scale by at least 6 points on the centile metric score over time
- Proportion of subjects with all R-ODS items above 0 at week 26
- Proportion of subjects requiring mechanical ventilation support (GBS DS 5)
  - Days on mechanical ventilation
  - Days in hospital and in an ICU
  - Changes in MRC sum score over time
- Pharmacokinetics (PK) parameters maximum serum concentration ( $C_{max}$ ), area under the curve (AUC), time to maximum plasma concentration ( $t_{max}$ ), terminal half-life ( $t_{1/2}$ ), V, clearance (CL), of imlifidase
- Pharmacodynamics (PD) effect on IgG following administration of imlifidase
- Pharmacodynamics (PD) effect on identified autoantibodies following administration of imlifidase
- Presence of anti-imlifidase antibodies (ADA)
- Quality of Life as measured by EurQol EQ-5D Health Questionnaire at 4 weeks and later

### **2.2.1 Exploratory Endpoint**

- Biomarker evaluation (analysis of anti-ganglioside antibodies and neurofilament light chain levels)

### 3. INVESTIGATIONAL PLAN

#### 3.1 Overall Study Design

**Figure 1. Overview of study design**

This is an open-label, single arm, multi-centre, phase II study of imlifidase in combination with standard care IVIg in subjects within 10 days of onset of GBS.

A detailed analysis plan is contained in the Statistical Analysis Plan (SAP). Data from each subject enrolled in this study will, if feasible, be compared with an external control group consisting of matched subjects from the IGOS database (Jacobs et al. 2017) (International Guillain-Barré Syndrome Outcome Study, ClinicalTrials.gov Identifier: NCT01582763). If such an indirect comparison study is feasible, details pertaining to the comparison will be outlined in a separate non-interventional study protocol.

##### 3.1.1 Screening

The study will recruit approximately 30 subjects with GBS eligible for IVIg treatment based on current practice (i.e. GBS disability score  $\geq 3$  at time of screening for enrolment and within 10 days of onset of weakness). Any male or female subject aged  $\geq 18$  years who presents with symptoms of GBS will be evaluated for eligibility to enter the study.

##### 3.1.2 Treatment

All subjects will receive imlifidase (Day 1) prior to standard care IVIg (see [Section 5.2](#)). Scores to assess disability status and capturing activities and social participation will be evaluated. Blood samples for safety, pharmacokinetics, and pharmacodynamics will be collected, and subjects will be closely monitored after infusion with imlifidase.

##### 3.1.3 Assessment Procedures

The subjects will be followed clinically on Days 1-8, 15, 29, 57, 92 and 180 days after imlifidase infusion and additionally with a 360-day telephone contact to assess GBS DS, R-ODS, capture health status in a questionnaire and AEs.

After study completion, all study subjects will be followed up regularly according to clinical practice at the site in question.

## **3.2 Safety Review Committee**

A Safety Review Committee (SRC) will be established to evaluate safety and tolerability data. The Committee will meet after the first subject has completed study visit 6 (Day 29) thereafter the SRC will meet after 3, 7 and 12 subjects have completed visit 6 (Day 29). A final SRC meeting will be held at the end of the study. The SRC will schedule a meeting as soon as possible if an important safety issue arises anytime during the conduct of the study. The SRC will comprise of 3 independent physicians. Internal and external experts will be invited to attend the meetings on an *ad hoc* basis, if any issue arises that requires additional expertise. A working procedure for the SRC will be described in an SRC Charter.

## **3.3 Study Timeline**

The expected study start is Q4 2019. Expected last subject last visit is Q2 2024 including recruitment and 12 months follow up for included subjects.

## **3.4 Planned Number of Study Sites and Subjects**

This is a multi-center study. Approximately 10 to 15 sites in Europe will be included. Approximately 30 adult male or female subjects will be enrolled in the study.

## **3.5 End-of-Study**

The planned end-of-study is defined as the last telephone contact has been completed (visit 10). Hansa Biopharma will ensure that an end-of-study notification is submitted to the concerned Regulatory Authority (RA) and Independent Ethics Committee (IEC)/ Institutional Review Board (IRB) according to local requirements.

For procedures in case of premature termination or suspension of the study, see [Section 13.4](#).

## 4. STUDY POPULATION

### 4.1 Selection Criteria

To be eligible for the study, subjects must meet all inclusion criteria and no exclusion criteria. Those subjects who pass the screening phase of the study will receive imlifidase. Imlifidase administration will commence as soon as possible after consent is obtained (within 24 hours) and within 12 days of onset of weakness due to GBS.

### 4.2 Inclusion Criteria

1. Signed Informed Consent obtained before any study-related procedures.
2. Willingness and ability to comply with the protocol.
3. Male or female aged  $\geq 18$  years at the time of screening.
4. GBS diagnosed according to National Institute of Neurological Disorders and Stroke (NINDS) diagnostic criteria (Asbury et al. 1990).
5. Onset of weakness due to GBS is not more than 10 days prior to screening.
6. Unable to walk unaided for  $>10$  meters (grade  $\geq 3$  on GBS DS).
7. IVIg treatment being considered.
8. Women of child-bearing potential willing or able to use at least one highly effective contraceptive method from the day of treatment until at least 6 months after the dose of imlifidase if not abstinent. In the context of this study, an effective method is defined as those which result in low failure rate (i.e. less than 1% per year) when used consistently and correctly such as:
  - combined (estrogen and progestogen containing) hormonal contraception associated with inhibition of ovulation
    - oral
    - intravaginal
    - transdermal
  - progestogen-only hormonal contraception associated with inhibition of ovulation
    - oral
    - injectable
    - implantable
  - intrauterine device (IUD)
  - intrauterine hormone-releasing system (IUS)
  - bilateral tubal occlusion
  - vasectomized partner
  - true abstinence: When this is in line with the preferred and usual lifestyle of the subject. Periodic abstinence (such as calendar, ovulation, symptothermal, post-ovulation methods) and withdrawal are not acceptable methods of contraception.

9. Men willing to use double-barrier contraception from the day of treatment until at least 2 months after the dose of imlifidase if not abstinent.

### 4.3 Exclusion Criteria

1. Previous treatment with imlifidase.
2. Previous IVIg treatment within 28 days prior to imlifidase treatment.
3. Subjects who are being considered for, or already on, PE.
4. Women of childbearing potential who are not willing to use contraception from the screening visit until at least 180 days following imlifidase dosing.
5. Breastfeeding or pregnancy.
6. Clinical evidence of a polyneuropathy of another cause e.g. diabetes mellitus (except mild sensory), alcoholism, vitamin deficiency, or porphyria.
7. Known selective IgA deficiency.
8. Hypersensitivity to IVIg or to any of the excipients
9. Immunosuppressive treatment (e.g. azathioprine, cyclosporine, mycophenolate mofetil, tacrolimus, sirolimus or >20 mg prednisolone daily) during the last month.
10. Subject known to have a severe concurrent disease, e.g. malignancy, severe cardiovascular disease and severe chronic obstructive pulmonary disease (COPD).
11. Any condition that in the opinion of the investigator could increase the subject's risk by participating in the study or confound the outcome of the study.
12. Known mental incapacity or language barriers precluding adequate understanding of the Informed Consent information and the study activities.
13. Subjects with clinical signs of ongoing infection.
14. Subjects should not have received other investigational drugs within 5 half-lives prior to imlifidase dosing.
15. Present or history of thrombotic thrombocytopenic purpura (TTP), or known familial history of TTP.
16. Positive PCR test for SARS-CoV-2 virus infection.

A subject will be withdrawn from the study if more than 12 days elapse between the onset of weakness and planned imlifidase administration, thus preventing that the administration of IVIg after imlifidase administration would be later than 14 days after onset of weakness.

### 4.4 Method of Assigning Subjects to Treatment Groups

Not applicable since this is a single-arm, non-randomised study.

## 4.5 Discontinuation of Subjects and Stopping Criteria

A subject will be withdrawn from the study if more than 12 days elapse between the onset of weakness and planned imlifidase administration.

The subjects have the right to withdraw from the study at any time for any reason without the need to justify their decision. However, the investigator should record the reason for the subject's withdrawal, if possible. The investigator also has the right to withdraw subjects. In either event, the investigator must notify Monitor.

Minor infusion-related reactions have been observed in some patients receiving imlifidase for other indications. These are usually mild and include chest discomfort, flushing, pharyngeal oedema and dyspnea. More severe reactions can occur.

If a minor infusion-related reaction (Common Terminology Criteria for Adverse Events (CTCAE) grade 1 or 2) is suspected the infusion should be temporarily stopped and the patient should be observed for clinical signs of allergic reactions. If a significant infusion-related reaction or anaphylactic reaction occurs (CTCAE grade 3 or higher) then the imlifidase therapy should be discontinued immediately.

The patient should be treated by the investigator according to local practice for an allergic reaction or a severe allergic reaction/anaphylaxis, respectively. If the symptoms resolve, the infusion can be resumed. If the symptoms persist or worsen, then the drug infusion should not be restarted.

A subject that prematurely discontinues participation must, if possible, be called in for a last visit and undergo the assessments and procedures scheduled for visit 9 (180 days after treatment with imlifidase). Even if the subject is not able to attend, the End-of-Study Form in the electronic Case Report Form (eCRF) must be completed. Subjects who for a medical reason cannot comply with the protocol procedures will be followed by best procedure to retrieve safety and efficacy data.

Subjects withdrawn from the study before visit 6 (29 days after treatment with imlifidase) may be replaced, not using the same subject number, in order to reach approximately 30 evaluable subjects.

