### **Visit 9, Day 180 (+14 days)**

The last on-site visit will be performed 180 days after infusion of imlifidase.

The following activities and assessments will be performed:

- Physical examination
- Pregnancy test (serum)
- ADA
- Exploratory biomarkers
- GBS DS, R-ODS and MRC sum score
- EurQol EQ-5D Health Questionnaire
- Confirm that the diagnosis is still GBS (yes/no), if no, specify which primary diagnosis the patient has been given

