### **7.2.2 Safety Local Laboratory**

Blood samples for safety laboratory evaluations of clinical chemistry and haematology parameters will be collected during study as described below. Actual sampling time will be recorded. Clinically significant abnormal findings will be reported as AEs. Findings at the

screening visit will be recorded in the medical history section in the eCRF. Clinical chemistry and haematology will be analysed locally.

Urine samples for safety evaluations will be taken as described below. Samples will be measured with dipstick and analysed locally. In case of abnormal results, a microscopic test will be measured.

The investigator will review the laboratory results and evaluate and document whether the results are normal or abnormal and whether abnormal results are non-clinically or clinically significant.

The following parameters will be collected:

- Clinical chemistry:
  - P-alanine aminotransferase (ALT), P-gamma glutamyl transferase, P-alkaline phosphate, P-bilirubin total, P-creatinine, P-potassium, P-albumin, P-calcium, P-immunoglobulin G (IgG)
- Haematology:
  - B-haemoglobin, B-haematocrit, B-white blood cell count, B-neutrophils (absolute count), B-lymphocytes (absolute count), B-eosinophiles (absolute count), B-platelet count
- Urinalysis(dipstick):
  - U-glucose, U-haemoglobin, U-protein, U-pH

Time of collection:

- All the above analyses:
  - At screening within 7 days prior to inclusion
  - Day 1: Prior to imlifidase administration
  - Days 2, 3 (prior to IVIg infusion), 8, 15 and 29

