### 7.2.4 Vital Signs

Blood pressure, pulse rate, respiratory frequency, oxygen saturation and body temperature will be assessed at:

- Screening

- Day 1:
  - Predose
  - 1 and 2 hours after end of imlifidase dosing
- Days 8, 15, and 29 (all except body temperature)

At Day 1 the subject will be observed for 2 hours after end of imlifidase infusion, longer if medically indicated. If the subject is without infusion related symptoms and vital signs are normal the observation period ends 2 hours after end of infusion.

Systolic and diastolic blood pressure will be measured after the subject has been in supine position for at least 5 minutes. All recordings will be performed using validated standard equipment. Clinically significant abnormal findings will be reported as AEs.

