#### **12.3.1.2 Treatment Emergent Adverse Event**

A treatment emergent adverse event is any adverse event occurring after the administration of the IMP and within the time of residual drug effect, or a pre-treatment adverse event or pre-existing medical condition that worsens in intensity after administration of the IMP and within the time of residual drug effect.

The time of residual drug effect is the estimated period after the administration of the IMP, where the effect of the product is still considered to be present based on pharmacokinetic, pharmacodynamic or other substance characteristics. The residual drug effect is generally accepted to be 5 times the terminal half-life. The terminal half-life of imlifidase is expected to be within the range of approx. 100 hours, i.e. in this study the residual drug effect is likely to be well within the Day 29 assessments, but since this is the first administration of imlifidase to GBS subjects, all AEs occurring up to Day 29 are regarded as treatment emergent.

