#### 4.8.2.2 Vital signs

Vital signs will be presented by visit (i.e., time point) for each parameter and summarised, including absolute change from baseline. Shift tables will be presented from baseline to all planned time points until end of residual drug effect, i.e. Day 29. Any changes from normal/low to high or from normal/high to low during these periods will be counted as a shift and will be summarised. The results will be flagged as Low (L)/High (H) as per the criteria defined in [Appendix 3](#).

In addition, separate listings containing vital signs data will be presented by subject.

The vital signs assessment part of visit 3, 7 and 9 has only been collected up to protocol version 7.0 (inclusive). Results from these visits will only be presented in the listing.

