#### 4.8.2.3 Clinical Chemistry, Haematology and Urinalysis

Laboratory tests will be summarised and presented in tables similarly as the vital signs parameters. In addition, shift tables for normal, abnormal and not clinically significant, abnormal and clinically significant results will be presented for all clinical chemistry and haematology laboratory parameters from baseline to all planned time points until end of residual drug effect, i.e. Day 29. Similar shift tables will be presented also for urinalysis parameters from baseline to all planned time points until end of residual drug effect, i.e. Day 29. Listings containing laboratory test data will be presented by subject. Abnormal clinically significant values will be flagged in listings.

The safety laboratory assessment part of visit 7 and 9 has only been collected up to protocol version 7.0 (inclusive). Results from these visits will only be presented in the listings.

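### The early-exit visit copies Visit 9, which since protocol v8.0 has no vital signs or safety laboratory, so a dosed subject leaving before Visit 6 has neither specified at exit

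*Protocol*

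**What the plan says.** Protocol 4.5 sets one exit schedule for all early leavers, whatever the day: "A subject that prematurely discontinues participation must, if possible, be called in for a last visit", at which the subject is to "undergo the assessments and procedures scheduled for visit 9 (180 days after treatment with imlifidase".

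Protocol 6.1 describes Visit 9 as the final on-site visit ("The last on-site visit will be performed 180 days after infusion of imlifidase"). It lists a physical examination, serum pregnancy test, ADA, biomarkers, GBS DS, R-ODS, MRC sum score, EQ-5D and confirmation of diagnosis. It lists no vital signs and no safety laboratory.

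The assessment sections agree. After the Day 1 pre-dose sample, Protocol 7.2.2 schedules the safety laboratory on "Days 2, 3 (prior to IVIg infusion), 8, 15 and 29". After Day 1, Protocol 7.2.4 schedules vital signs on "Days 8, 15, and 29 (all except body temperature"). The flow chart also ends both at Day 29.

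The SAP shows that this was a change. SAP 4.8.2.3: "The safety laboratory assessment part of visit 7 and 9 has only been collected up to protocol version 7.0 (inclusive"). SAP 4.8.2.2: "The vital signs assessment part of visit 3, 7 and 9 has only been collected up to protocol version 7.0 (inclusive"). Both sections add that results from those visits go to listings only.

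On the safety window, Protocol 12.3.1.2 says that "all AEs occurring up to Day 29 are regarded as treatment emergent". The vital-sign and laboratory shift tables also stop at Day 29.

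**The concern.** Dropping laboratory tests and vital signs at Day 180 can be reasonable for someone who has completed six months. The revision history gives a rationale for v8.0: more safety knowledge, and close monitoring under standard of care. That rationale does not obviously extend to a subject leaving in the second or third week, yet 4.5 still points every leaver to the reduced visit.

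The documents themselves say why late values inside the window matter. Protocol 1.4 names infection risk after IgG removal and, for IVIg, neutropenia, worsening renal failure and thromboembolic events. Protocol 9.5 makes severe or serious infection within 30 days an event of special interest. IgG, neutrophils and creatinine are all in the 7.2.2 panel, but the exit visit does not call for them. Clinically significant laboratory and vital-sign findings are to be reported as adverse events (7.2.2, 7.2.4, 9.2.3), so an abnormality that is not measured may also go unreported as an event. Missing values are not imputed (SAP 4.1.3).

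**Working it through.** The plan states no figure to reproduce: there is no formal sample size calculation and no hypothesis test. The check sets the exit rule beside the schedules and counts how old the last scheduled value would be.

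**Inputs**
- Safety laboratory (7.2.2): Day 1 pre-dose, then Days 2, 3 (before IVIg), 8, 15, 29.
- Vital signs (7.2.4): Day 1 pre-dose and 1 h and 2 h after the end of infusion, then Days 8, 15, 29.
- Exit visit content (4.5 with Visit 9 in 6.1): neither of these.
- Half-life behind the window (12.3.1.2): about 100 h, multiplied by 5.

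**Window.** 5 x 100 h = 500 h, and 500 / 24 = 20.8 days. The documents extend this to Day 29 for reporting, so Day 29 is their own limit and is wider than the half-life arithmetic.

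**Age of the last scheduled value.** For exit on day d, age = d minus the last scheduled day before d. Nominal days are used and visit windows are ignored.

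| Exit day | Last laboratory | Age (days) | Last vital signs | Age (days) |
|---|---|---|---|---|
| 2-3 | Day 1 pre-dose, or Day 2 | 1 | Day 1, 2 h after infusion | 1-2 |
| 4-7 | Day 3, before IVIg | 1-4 | Day 1, 2 h after infusion | 3-6 |
| 8, Visit 4 not done | Day 3, before IVIg | 5 | Day 1, 2 h after infusion | 7 |
| 9-14 | Day 8 | 1-6 | Day 8 | 1-6 |
| 15, Visit 5 not done | Day 8 | 7 | Day 8 | 7 |
| 16-28 | Day 15 | 1-13 | Day 15 | 1-13 |

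Examples: exit on Day 7 gives 7 - 3 = 4 days for laboratory and 7 - 1 = 6 days for vital signs. Exit on Day 28 gives 28 - 15 = 13 days for both.

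**What the exit rule itself costs.** An exit sample would add one value per parameter. It would not recover the scheduled visits that the subject never reached. The loss due to the rule is therefore one late set of values per leaver.

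**How many subjects.** The documents give no withdrawal rate. Assuming 0-10% before Day 29, the count is 0 x 30 = 0 to 0.10 x 30 = 3.

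**Placement in the tables.** SAP 4.8.2.2 and 4.8.2.3 tabulate planned time points up to Day 29. An exit value from, say, Day 21 belongs to none of them, and neither section says where it would go. If exit data were recorded as Visit 9, both sections would send them to listings only, although they come from inside the window.

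**The case against.** The strongest reply is that several provisions already cover these subjects. The exit visit includes a physical examination with cardiovascular, respiratory and neurological components (7.2.3). Adverse events leading to discontinuation are followed until they resolve or stabilise (9.2.4). Subjects who cannot comply for a medical reason are followed to retrieve safety data (4.5). All of this stands and reduces the practical risk. None of it specifies a laboratory or vital-sign measurement at exit.

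Three stronger readings are tempting, and the documents do not support them.

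- A reader might infer that early leavers have no laboratory or vital-sign data. They keep every scheduled value obtained before exit. Someone leaving on Day 10, for instance, should have Visit 4 data, because that visit is Day 8 with a window of +2 days.
- A reader might blame the rule for three of the five post-dose laboratory time points (Days 8, 15, 29) when a subject leaves between Day 3 and Day 8. Those are lost because the subject left. The SAP's shift tables cover all planned time points up to Day 29, so leavers still contribute where they were measured.
- A reader might infer that replacing subjects withdrawn before Visit 6 hides the loss. A dosed subject stays in the safety set (Protocol 12.1.3, SAP 3.3), the replacement takes a new subject number (4.5), and withdrawals are reported by reason and listed by subject (SAP 4.2, 4.4).

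Nor do the documents show that early leavers are more likely to have had a safety problem; 4.5 allows withdrawal for any reason.

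Timing also counts against the point. SAP v2.0 was updated during the main analysis, and Protocol 14.1 bases that analysis on all patients having had Visit 9. On that sequence no subject is still short of Visit 6, and a new protocol sentence would change no data collection in this trial.

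**Conclusion.** The gap is real but narrow. Under v8.0 and v9.0, following 4.5 as written gives a dosed subject who leaves before Visit 6 no specified laboratory or vital-sign measurement at exit, while the documents' own safety window is still open. Under v7.0, Visit 9 included both, so the gap does not apply to subjects managed under that version.

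In size, it is one late set of safety values per leaver, for an assumed 0 to 3 of 30 subjects. No estimate, test or analysis-set membership changes. The ages in the table rest on nominal visit days and on no unscheduled measurement being taken at exit; sites may well take one under standard care, but the protocol does not ask for it.

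The statement that safety parameters are measured up to Day 180 (Protocol Synopsis, Study Procedures/Assessments; SAP 2.1) also needs reconciling with the visit lists. It fits the physical examination and ADA, which SAP 1.1.2.2 counts as safety, but not vital signs or the safety laboratory.

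Severity: minor. It is a cheap improvement.

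**What to change.** Reconcile Protocol 4.5 with the Visit 9 list in 6.1, with 7.2.2 and 7.2.4, and with the Day 180 statement in the Synopsis and SAP 2.1. Specify in 4.5 that a dosed subject who leaves before Visit 6 has the Visit 6 vital signs and safety laboratory at the last visit, in addition to the Visit 9 assessments, and add a matching flow-chart footnote. The Visit 6 vital signs exclude body temperature, so the sentence should say whether that exclusion is intended at exit.

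In SAP 4.8.2.2 and 4.8.2.3, show exit values in a separate 'last on-study' row by actual study day. Do not count them as Day 29, and do not leave them in listings only. This also covers any exit values already recorded under v7.0 or taken locally.

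The cost is one sentence, one footnote and one table row, plus one local blood and urine sample and one set of vital signs for a few subjects who are already attending and already giving blood for ADA and biomarkers. If every subject is already past Visit 6, only the SAP row can act in this trial, and the protocol wording serves any later study that reuses this text.
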